The purpose of the current study is to further elucidate the underlying mechanisms of increased sensation and pain relief observed in patients receiving treatment with the PROVANT[®] Therapy System. In vitro studies have provided evidence that PEMF therapy improves nerve growth and may improve nerve function through up-regulation of genes involved in neurogenesis. [Data on File] In addition, genes related to angiogenesis have also been shown to be up-regulated. Through evaluation of vibration perception threshold, nerve conduction velocity, quantitative sensory testing, vascular changes (skin perfusion pressure), blood glucose (hemoglobin A1c), and quality

of life questionnaires, this study will evaluate if PEMF treatment in vibration perception and skin perfusion is enhanced in subjects that receive treatment with Provant compared to a group of subjects that receive treatment with a sham device.

II. STUDY OBJECTIVES

This study is designed to evaluate the effectiveness of the PROVANT[®] Therapy System (PEMF) in changing Vibration Perception Threshold (VPT) and Thermal Sensory Perception using Quantitative Sensory Testing (QST) in patients with bilateral symmetrical diabetic peripheral neuropathy (DPN) when treatment is administered twice daily through a 120-day period.

III. STUDY DESIGN

A. Study Design

The study is a multi-center, sham-controlled, double-blind, enriched enrollment randomized withdrawal study of the safety and efficacy of multi-dose PEMF therapy on subjects with bilateral symmetrical DPN. A graphic presentation of the study design is shown in Figure 1.

25

B. Efficacy Endpoints

This study will evaluate the changes in vibration perception threshold, thermal sensory perception, nerve conduction velocity, skin perfusion pressure, pain intensity, brief pain inventory, brief fatigue inventory, PGIC, hospital anxiety and depression scale, and neuropathy specific quality of life.

C. Safety Evaluation

All observed and reported adverse effects will be recorded by the research staff. Start dates, end dates, frequency, severity of the event, any treatment required to treat the event, and the investigator's judgment on causality and relationship to the study device will be assessed for each AE. Any AE occurring after the signing of the informed consent form will be recorded. Only those AEs occurring after initiation of the first treatment with the study device will be considered treatment-emergent AEs.

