Adverse events will be mapped to preferred terms and body systems using the Medical Dictionary for Regulatory Activities (MedDRA) coding dictionary. While the primary presentation of adverse events will be subject-based, the number of adverse events will also be reported. The number and percentage of subjects reporting each event will be summarized during the treatment period by treatment assignment. Incidence of adverse events by maximum reported severity will also be tabulated. Serious adverse events and adverse events leading to discontinuation will be displayed.

D. Eligibility Criteria

Eligibility for participation in this study will be based on the inclusion/exclusion criteria. An individual subject may only be included in the study once.

1. Inclusion Criteria

- 1. Subject age is greater than or equal to 22 years and less than 80 years of age.
- 2. Subject has documented Type 1 or Type 2 diabetes mellitus (receiving insulin, diet controlled, or taking parenteral hypoglycemic agents)
- 3. Subject is on a stable antidiabetic regimen (medication and/or diet) to control their diabetes for at least 30 days prior to Screening.
- 4. Subject has an HbA1c <10% at Screening or within 2 months of Screening.
- 5. Subject has daily pain attributed to bilateral symmetrical Diabetic Peripheral Neuropathy with numbness, tingling, and/or burning based on clinical judgement for at least 6 months prior to screening.
- 6. Subject's pain or discomfort from DPN is identifiable.

- 7. Subject is in pain Phase 2, 3, or 4 as per the Phasing of Neuropathy Scale.
- Subjects average pain over the last 24 hours is ≥3 based on the 11-point Numeric Pain Rating Scale (NPRS) at the Screening Visit.
- 9. Subject has adequate lower extremity pulse in both feet and no intermittent claudication.
- 10. Subject is able to ambulate independently with assistive devices, but not wheel chair bound.
- 11. Subject is willing and able to give written informed consent and to comply with all parts of the study protocol.
- 12. Female subjects must be post-menopausal, surgically sterile, abstinent, or practicing (or agrees to practice) an effective method of birth control if they are sexually active for the duration of the study (Effective methods of birth control include prescription hormonal contraceptives, intrauterine devices, double-barrier methods, and/or male partner sterilization).

2. Exclusion Criteria

- 1. Subject is in pain Phase 1 or 5 as per the Phasing of Neuropathy Scale.

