The PROVANT[®] Therapy System is a solid-state, fixed-power output radio frequency generator and transmitter designed to operate at the Federal Communication Commission (FCC) authorized medical device frequency of 27.12 MHz. The primary components are the control unit, the treatment applicator that generates and delivers the shortwave RF energy, and single-use Disposable Applicator Covers (DACs) intended to minimize contagion transmission and help protect the treatment applicator from biological contamination. Key functions and features of these components are as follows:

1. Control Unit

The control unit contains the main electronics, software, and user interface of the system. The control panel has a therapy Start/Stop switch and two therapy status indicators, described below, which are located on the top of the control panel, as well as a usage meter on the side of control panel.

Pressing the therapy Start/Stop switch initiates a preset, thirty (30)-minute therapy session by starting the Radio Frequency Identification Device (RFID) tag interrogation and treatment sequence described in greater detail below. Pressing the therapy start/stop

switch again after a therapy session has started will stop the RF energy generation. When pressed, the therapy Start/Stop switch generates an audible tone to inform the user that therapy is being initiated or terminated.

The two-therapy status indicators on the control panel indicate when therapy is underway and the amount of time (in minutes) remaining in the therapy session. When treatment is initiated, the message "CPI RUNNING" is displayed and green bars scroll from left to right across the indicator window. When the thirty-minute therapy session is concluded, the generation of RF energy is automatically terminated, the therapy status indicator windows go blank, and a brief audible beep is generated to alert the user that the treatment is finished. The user will then be instructed to turn off the power switch, remove the used Disposable Applicator Cover, and store the treatment applicator and cable until the next use.

In this study, the subject will treat both feet for 30 minutes, twice a day for the first 60 days (and up to 90 days) with active devices, and then continue to treat after randomization until Day 120. Response to treatment for randomization will be assessed at Days 61, 75, or 91.

2. Disposable Applicator Covers.

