The label on each study device kit will contain the protocol number and kit number. There will be sufficient space for study personnel to write the subject number, date dispensed, and the initials of the dispenser on the distribution label.

J. Preparation and Administration

Each subject will receive two devices to use during the study. Each treatment session with the study devices will be 30 minutes in duration. All treatment sessions will be self-administered by the subject or his/her family or caregiver in the home or similar setting.

The first treatment with the study devices will be administered on the morning of the day following the Enrollment Visit (Day 1) at 8am (\pm 2 hours). Subjects will assume a comfortable position and place their feet (both feet will be treated) on the treatment applicators of the PEMF devices, centering the applicators under the plantar surface (bottom of foot) of each foot as identified by the investigator. Treatment will be administered continuously for 30 minutes on both feet simultaneously. Thereafter, subjects will self-administer treatments twice daily, at 8am (\pm 2 hours) and 8pm (\pm 2 hours) up to Day 120 (Day 91 for non-responders).

Prior to initiation of each treatment session, the subject will take the treatment applicator of each study device and insert it into a new Disposable Applicator Cover. When inserted properly, the yellow starburst logo on the treatment applicator is aligned with the same logo on the Disposable Applicator Cover, and the words "This side towards patient" will be visible through the clear window of the Disposable Applicator Cover. When applied to the subject's feet, the side of the treatment applicator with the yellow starburst logo is directed toward the bottom of the foot (plantar surface). Further directions for use for the PEMF system are found in the Instruction Manual. Upon completion of the treatment session, the subject will remove and discard the Disposable Applicator Covers, and store the PEMF devices until the time of the next scheduled treatment session. Disposable Applicator Covers may be discarded as standard waste.

K. Blinding

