At the start of this study, all subjects will receive active devices. At Day 61, Day 75, or Day 91, if the subject becomes a responder based on a 1-point decrease in the average pain score using the Numeric Pain Rating Scale, the subject will be randomized 1:1 (active: sham). The sham devices will be PEMF devices that are de-activated such that no radiofrequency energy is generated or delivered when the device is started. All other functions, including the start sequence, display lights, audible start-beep and fan operation of the sham devices are identical to that of the active PEMF devices. Sham devices are indistinguishable from the active PEMF devices being used in the study. The subjects, research personnel at the investigative site, and sponsor will be fully blinded to the randomization assignment and unable to differentiate active and sham devices.

L. Study Assessments

All efficacy outcome measures will be assessed in order to allow for characterization of the response to PEMF therapy. All efficacy assessments will be conducted at the Enrollment Visit (Baseline; Day 0) and at the end of study visit (Day 121).

1. Primary Efficacy Assessments

Vibratory Perception Threshold (VPT): For large nerve fiber assessment. VPT is a non-invasive test used in quantifying sensation/sensitivity to vibration in evaluating sensory dysfunction associated with diabetic neuropathy. The hand-held vibratory stimulator will be placed against the midpoint of the plantar aspect and big toe of the right foot; the tester will initiate the automated test that will last between 5-10 minutes. Three tests will run at each location and the average of the 3 will be populated by the system. The VPT will be collected using the VSA-3000 Vibratory Sensory Analyzer at the midpoint on the plantar aspect and on the big toe of the right foot. VPT will be collected at the Enrollment Visit to obtain a baseline value and on Days 15, 30, 45, 61, 75, 91, 105 and 121.

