In a single question, subjects will be asked to describe their overall status compared to the start of the study ("Since the start of the study, my overall status is:"), and to score it as either very much worse, much worse, minimally worse, no change, minimally improved, much improved or very much improved (Appendix C). "Much Improved" and "Very Much Improved" are considered clinically meaningful results.¹ PGIC will be collected in the paper diary every 7 days immediately following the morning treatment during the 120-day treatment period. PGIC serves to anchor within-subject changes in pain over the course of treatment.

Hospital Anxiety and Depression Scale (HADS): is a patient reported assessment that detects stats of depression and anxiety. The subscales within the assessment assess the severity of the emotional disorder connected to having diabetic peripheral neuropathy. Subjects will complete the assessment at the Enrollment Visit, Days 30, 61, 91, and end of study visit (Day 121).

NeuroQoL: is a validated measure that measures the effects of diabetic peripheral neuropathy and its complications on an individual's quality of life. The questionnaire will be completed by the subject at the Enrollment Visit and end of study visit (Day 121).

3. Exploratory Efficacy Assessment

Biopsy: To assess c-fiber nerve density when treatment with Provant is administered. Biopsies will be taken from subjects that consent to them being taken. At least 2 subjects per pain phase category will be consented. One biopsy will be obtained at the distal leg, 10cm above the lateral malleolus on the right leg. A second biopsy will be obtained at the distal thigh, 10cm above the superior margin of the patella on the right leg. Both biopsies will be taken at the Enrollment Visit. The biopsies will be shipped overnight to the central lab. At the Day 121 Visit, a second set of biopsies will be obtained to the right of the baseline biopsies on the same subjects that consented at enrollment and shipped overnight to the central lab. At the end of the study, the biopsies will be compared to assess nerve fiber density.

4. Additional Study Assessments

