Subject adherence (compliance with twice daily treatment with the study device) will be assessed during the interim visits by viewing the usage meter on each device, and upon completion of the treatment period at the Day 121 visit by the research staff reading and recording the number displayed on the study device usage meter. The usage meter will read 0.0 at Enrollment and upon randomization and will increase by 0.5 for each complete 30-minute treatment. A subject with complete adherence will be expected to have a usage meter reading based upon their response date.

Subjects will be instructed to return all unused DACs at the end of treatment visit. Each treatment session requires one new DAC, thus in the course of 120 days of treatment, the subject will utilize up to 240 DACs. If a subject is determined to be a non-responder at Day 91, they will utilize 180 DACs per PEMF device (360 total).

M. Protocol Adherence

Strict adherence to all specifications laid down in this protocol is required for all aspects of the study conduct. If protocol modifications are necessary, all alterations that are not solely of an administrative nature require a formal protocol amendment.

If an investigator has deviated from the protocol in order to eliminate an immediate hazard to subjects or for other inevitable medical reasons, the investigator shall document all such deviations, including the reasons thereof, and immediately submit the documentation to the sponsor and to the IRB if required.

N. Concomitant Medications

All concomitant drug and non-drug treatments as well as the frequency of administration and indication for the treatment will be recorded in the subject's chart. Additions to the subject's therapeutic regimen (agent, dose, frequency of administration) for treatment of diabetic peripheral neuropathy (other than the introduction of PEMF therapy) will not be allowed through Day 121 of the study. Subjects will be allowed to continue administration of prn medications on an *ad lib* basis. Subjects may choose to reduce or discontinue opioid or other drug therapies during the treatment period of the study.

It is important to record the reason why each analgesic is being taken by the subject, specifically analgesics taken for treatment of pain associated with diabetic neuropathy. Analgesics taken for other reasons, e.g., headache, will be collected through recording of concomitant medications in the subject's chart.

1. Allowed Medications

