- Request for withdrawal by the subject for reasons other than an intolerable AE.
- Lost to follow-up, as determined by failure to respond to at least 2 telephone calls followed by certified letter sent to the subject's last known address. All attempts to contact the subject must be documented in the subject's source documents.

VI. STATISTICAL CONSIDERATIONS

The statistical analysis of the study is described in detail in a separate version-controlled prospective Statistical Analysis Plan (SAP). However, the statistical methodology described in this section of the protocol will be the basis for the detailed SAP.

This bi-phasic design includes 2 sequential periods: the *Induction Phase* and *Randomized Withdraw Phase*. All safety analyses will be performed on the *Safety Analysis Set*, defined as all subjects who were enrolled into the study and issued study devices during the *Induction Phase* and followed through the *Randomization Withdraw Phase* or until they withdraw. Once a subject is determined to be eligible, the subject will be issued active treatment devices and the subject will be formally enrolled into the study and become part of the *Safety Analysis Set*. Where not otherwise specified, the last pre-treatment observation will be used as baseline for calculating post-treatment changes from baseline.

A. Induction Phase / Baseline Evaluations

Prior to study treatment, subjects will complete the baseline health economic questions, including the Brief Pain Inventory (BPI), Brief Fatigue Inventory (BFI), Hospital Anxiety and Depression Scale (HADS), and the NeuroQoL. Vibration Perception Threshold (VPT), Quantitative Sensory Test (QST) and Nerve Conduction Velocity (NCV) will be completed. Skin Perfusion Pressure

(SPP) will be performed to obtain a baseline value of the plantar and dorsal aspect of the right foot. Once the subject is determined to be eligible, the subject will be issued active treatment devices and the subject will be formally enrolled into the study and become part of the *Safety Analysis Set*.

Subjects in the *Safety Analysis Set* will be instructed in the use of the devices for 60 days in the home environment. At Days 15 and 45, subjects will return to the clinic to have the VPT and QST conducted. Subjects will return to the clinic at days 30 and 61 for evaluation and complete questionnaires.

B. Randomized Withdraw Phase

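### Adverse-event tables by group count from the first active induction treatment, so the sham column carries 60 to 90 days of active-device events and never-randomised subjects have no column

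*Combined protocol and SAP*

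**What the plan says.** Three adverse-event summaries name a group. Section III.C gives the main one: "The number and percentage of subjects reporting each event will be summarized during the treatment period by treatment assignment". Section VI.D adds two more, both per treatment group: subjects with at least one event, and the number of events. III.C makes the subject-based presentation the primary one.

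VI.D bases every adverse-event summary on treatment-emergent events, and III.C defines these: "Only those AEs occurring after initiation of the first treatment with the study device will be considered treatment-emergent AEs". That first treatment is never sham. III.K states: "At the start of this study, all subjects will receive active devices". III.G.1 gives the length of this exposure: "twice a day for the first 60 days (and up to 90 days) with active devices".

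The protocol uses the term treatment period for the whole course. III.L.2 says of the global impression score: "PGIC will be collected in the paper diary every 7 days immediately following the morning treatment during the 120-day treatment period".

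Section VI applies all safety analyses to the Safety Analysis Set, "defined as all subjects who were enrolled into the study and issued study devices" in the Induction Phase. The set therefore includes Day 91 non-responders, who leave without being randomised, and anyone who withdraws earlier.

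Section VI names the two phases, but III.C and VI.D do not use them. No section restarts the count at randomisation, assigns an event to the device in use at onset, or says where never-randomised subjects go in a by-group table.

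**The concern.** A subject assigned to sham has spent at least half of the 120 days on an active device. If the count starts at the first induction treatment, events from that time fall in the sham column. The active and sham columns then share much of the same exposure, and a real difference in either direction looks smaller as a ratio and as subject-level incidence.

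The post-randomisation period gives the only blinded comparison of device with sham on safety. Several anticipated effects listed in X.B (tingling, numbness, burning, worse pain) resemble the disease itself, so a reader needs to know which device the subject was using when an event began. The planned by-group tables cannot show that. They also leave undefined the place of subjects who used only active devices and were never assigned.

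**Working it through.** The plan gives no adverse-event rate, power or safety calculation, so it has no figure of its own to reproduce. The check takes the exposure implied by the schedule and applies the counting rule to it.

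**1. Exposure.** Randomisation is at Day 61, 75 or 91 (III.K). Treatment starts on Day 1 and runs "up to Day 120 (Day 91 for non-responders") (III.J). Let T = visit day − 1 be the active days before randomisation, and S = 120 − T the days after.

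| | Day 61 | Day 75 | Day 91 |
|---|---|---|---|
| T | 60 | 74 | 90 |
| S | 60 | 46 | 30 |
| T/120 | 50.0% | 61.7% | 75.0% |

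With the full +3-day visit window the shares are 63/120 = 52.5%, 77/120 = 64.2% and 93/120 = 77.5%.

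**2. Event-rate ratio.** Assume a constant rate L on active and L/R on sham. Expected events per subject are 120L in the active column and (T + S/R)L in the sham column, so the tabulated ratio is 120/(T + S/R). For R = 2 at Day 61 this is 120/(60 + 30) = 1.33.

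| True ratio R | Day 61 | Day 75 | Day 91 |
|---|---|---|---|
| 1.5 | 1.20 | 1.15 | 1.09 |
| 2 | 1.33 | 1.24 | 1.14 |
| 3 | 1.50 | 1.34 | 1.20 |
| no events on sham (120/T) | 2.00 | 1.62 | 1.33 |

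The last row is a ceiling and needs no assumed event rate. The expected difference in counts is 120L − (T + S/R)L = SL(1 − 1/R), the same as after randomisation alone.

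**3. Noise.** With Poisson counts, the SD of the count difference relative to that of post-randomisation events alone is √[(120 + T + S/R)/(S + S/R)]. Event rate and arm size cancel. For R = 2:
- Day 61: √(210/90) = 1.53
- Day 75: √(217/69) = 1.77
- Day 91: √(225/45) = 2.24

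**4. Subject-level incidence.** Assume 60-day risks of 20% on active and 10% on sham, with constant hazards. Active over 120 days: 1 − 0.8² = 36.0%.
- Day 61: sham is 1 − 0.8 × 0.9 = 28.0%. The table shows a difference of 8.0 points (ratio 1.29). Post-randomisation events alone give 20.0% versus 10.0% (10.0 points, ratio 2.00).
- Day 91: sham is 1 − 0.8^1.5 × 0.9^0.5 = 32.1%. The table shows 3.9 points (ratio 1.12). Post-randomisation events alone give 10.6% versus 5.1% (5.4 points, ratio 2.06).

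In general the tabulated risk difference is exp(−T × active hazard) times the post-randomisation one. Over assumed pairs of 10% vs 5%, 20% vs 5%, 20% vs 10%, 30% vs 10% and 40% vs 20%, it shrinks to between 46% and 90%.

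**5. Sham subjects already counted from induction.** With R = 2, the share is (1 − e^(−TL))/(1 − e^(−(TL + SL/2))). For assumed L of 0.0005 to 0.005 per day it is 67% to 72% at Day 61 and 86% to 89% at Day 91.

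**6. Never-randomised subjects.** Assume 40 enrolled, n randomised at Day 61, and the rest treated for 90 days. IV.L supports the 90 days: "If a subject is determined to be a non-responder at Day 91, they will utilize 180 DACs per PEMF device (360 total"), and 180/2 per day = 90. Active-device subject-days are (n/2) × 120 in the active column, (n/2) × 60 in the sham column and (40 − n) × 90 with no column.

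| n | Active column | Sham column | No column |
|---|---|---|---|
| 40 | 2,400 (67%) | 1,200 (33%) | 0 |
| 30 | 1,800 (50%) | 900 (25%) | 900 (25%) |
| 20 | 1,200 (33%) | 600 (17%) | 1,800 (50%) |

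At n = 30 the sham column holds 900 active-device days beside 15 × 60 = 900 true sham days.

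**The case against.** **The SAP may already do this.** Section VI defers detail to a separate SAP, and table columns and onset attribution are ordinary SAP content. This stands as a limit: that document was not available. But Section VI makes the protocol's own methods the basis for it, and those methods contain no split to carry forward.

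**VI.D mentions active or sham.** The summary of relationship to the device carries those words in parentheses, which could mean that each event is tied to one device. The phrase is ambiguous, sets no onset rule and does not govern the three by-group counts.

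**Randomisation balances induction events.** True in expectation, so the difference in event counts is unbiased. Ratios and subject-level incidence still move toward no difference, and noise rises.

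**The scenarios all put active above sham.** Worse pain could be commoner after withdrawal to sham. The attenuation works both ways: at R = 0.5 and Day 61 the tabulated ratio is 120/(60 + 120) = 0.67, so a sham-side excess is hidden too. At R = 1 there is nothing to dilute.

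**The rates are assumed, and effects may cluster early.** The size is indeed illustrative. If events cluster in the first weeks on active, the post-randomisation table may show little contrast even after the change.

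**The study is small and descriptive.** No formal testing or power is planned. Start dates and listings by relative study day allow events to be sorted by hand, so no data are lost. That limits the seriousness; it does not make the planned tables adequate.

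**Conclusion.** The concern holds on the supplied text, and the tables should be changed. The stated rules place 60, 74 or 90 days of active-device events in the sham column and give never-randomised safety-set subjects no column in the by-group tables. Those subjects do remain in the ungrouped summaries and listings.

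The exposure shares follow from the schedule alone. The ceiling on the rate ratio needs only a constant active rate. The other figures rest on assumed rates, ratios or numbers randomised, which the documents do not give. The severity, serious-event and discontinuation summaries name no arm. Only if the severity and relationship tables are also shown by arm could VI.D's rule of counting each subject once, at the worst severity or strongest relationship, let an induction event set a sham subject's entry.

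Confidence is medium, because the separate SAP could add the split. The randomised safety comparison stays descriptive and imprecise with or without it.

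**What to change.** In III.C, VI.D and the SAP, tabulate adverse events by phase and by device in use at onset:

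- **Induction Phase:** one active-device column for the whole Safety Analysis Set, including subjects never randomised.
- **Randomized Withdraw Phase:** active versus sham, counting events with onset or worsening after first use of the randomised device. Show subject-days of exposure, because randomised exposure ranges from 30 to 60 days.
- Apply the count-once rules within each phase.
- State that active or sham in the relationship summary means the device in use at onset.
- Use the same split for serious events and for events leading to discontinuation.

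The cost is a wording change and one extra table set. Start dates are already recorded under III.C, so no new data are needed. The downside is fewer events in the randomised comparison.
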